Protocol Title:

Double-Blinded Randomized Control Trial Comparing Liposomal Bupivacaine and Bupivacaine Hydrochloride in Transversus Abdominis Plane Blocks Prior To DIEP Flap for Breast Reconstruction

Protocol Version Date:

10/01/2018

NCT # 03700970

Principal Investigator:

[name] – Professor, Department of Plastic Surgery, Vanderbilt University Medical Center
[name]

Sub-Investigators:

[name] [name] – Assistant Professor, Department of Anesthesiology, Vanderbilt University Medical Center
[name] [name] – Professor, Department of Anesthesiology, Vanderbilt University Medical Center
[name] – Associate Professor, Department of Plastic Surgery, Vanderbilt University Medical Center
[name] – Department of Plastic Surgery, Vanderbilt University Medical Center

Background

Perioperative and postoperative analgesia is a high priority for patients undergoing plastic and reconstructive surgery. It is of particular interest in patients undergoing abdominally-based free flaps for breast reconstruction (e.g., deep inferior epigastric artery perforator flaps) that includes excision of abdominal skin and subcutaneous tissue since the majority of pain after these operations is derived from the abdominal donor site (Jablonka et al, PRS 2017). Although intravenous and oral opioids have been the mainstay of postoperative pain control for this patient population, they are associated with a number of detrimental effects that can delay recovery and increase length of hospital stay. For example, they can lead to nausea, vomiting, constipation, lethargy, cough suppression, confusion, and orthostatic hypotension (Pizzi et al; Pharmacotherapy 2012). By reducing these side effects, resumption of a normal diet and ambulation can be achieved faster, which can accelerate recovery. This in turn can lead to decreased length of hospital stay and its associated cost, as well as improvement in the perceived quality of life for this patient population.

Local analgesia, in the form of transversus abdominis plane (TAP) block that is administered in the operating room prior to the incision under ultrasound guidance, has been advocated to provide improved analgesia in the perioperative and postoperative periods. This is a promising approach that can decrease or even eliminate the need for narcotics in the postoperative period. This is a standard procedure at VUMC, and part of the Enhanced Recovery Pathway, for patients undergoing abdominally-based free flap breast reconstruction. However, there is debate regarding the best local anesthetic for these purposes. Liposomal bupivacaine has been used widely and is believed to provide adequate analgesia for more than 48 hours after surgery. On the other hand, plain bupivacaine is significantly cheaper and has also been shown to have promising and lasting analgesic results. To date, there are not randomized trials comparing the two local analgesics in a well-defined group of plastic surgery patients in general and also specifically in patients undergoing abdominally-based free flap breast reconstruction.

Rationale and Specific Aims

This study is designed to compare the efficiency of TAP blocks using liposomal bupivacaine versus plain bupivacaine that is administered in the operating room under ultrasound guidance prior to the incision in patients undergoing abdominally-based free flap breast reconstruction.

The ***primary aim*** of the study will be to compare the amount of supplemental postoperative narcotic analgesia (both intravenous and oral) required by the study groups in oral morphine equivalents from postoperative days 0 to 7. The amount of postoperative analgesia will be documented daily until postoperative day 7. It will be obtained from the medical records during hospitalization, and with daily phone calls after the patients get discharged with instructions to document this data daily.

The *secondary aims* will be:

- 1) Pain control, as measured by a visual analog NPS number ranging from 0 (no pain at all) to 10 (worst pain ever) between the 2 groups. This will be evaluated immediately after surgery in the postanesthesia care unit (PACU), on the day of surgery and all subsequent postoperative days until discharge and on postoperative day 7. In the PACU patients will be asked about their current pain. For the inpatient postoperative days and postoperative day 7, patients will be asked to record their average, current, and maximum Numeric Pain Scale (NPS) score for the previous 24 hours
- 2) Time to first opiate use: time from end of surgery (i.e. patient went to recovery or ICU) until time of first opioid intake)
- 3) Time to return of bowel function: time from end of surgery (i.e. patient went to recovery or ICU)
- 4) Incidence of narcotic complications (i.e. nausea, vomiting, constipation, urinary retention, dizziness, etc.); defined as the number of occurrences of the complication per day for the first 7 days after surgery
- 5) Quality of life (QoL) as measured with:
Baseline (during consenting before surgery): WHODAS, QoR-15, PROMIS-29
0-7 days: QoR-15
Day 7 and 14: PROMIS-29
Day 30: PROMIS-29, WHODAS

Inclusion/Exclusion Criteria

Inclusion criteria will include:

- 1) age between 18-85 years
- 2) males or females
- 3) plastic surgery for abdominally-based free flap breast reconstruction.

Exclusion criteria will include:

- 1) those not candidates for TAP blocks due to allergies to the medications (e.g., bupivacaine)
- 2) those with anatomic contra-indications to performing a TAP block
- 3) those unwilling to participate in follow-up assessments
- 4) vulnerable populations
- 5) chronic pain or associated diagnosis

Enrollment/Randomization

Patients undergoing abdominally-based free flap breast reconstruction under general anesthesia will be randomized to receive a TAP block with either liposomal bupivacaine or plain bupivacaine to determine if narcotic requirements and/or pain control is better achieved with one of the above methods. Patients in this study will be recruited in the plastic surgery outpatient clinics. No advertising will be done and there will be no recruitment tactics.

Patients eligible for the study will be seen by the participating attendings at Vanderbilt University Medical Center, or one of their associates. The patient will be told about the study and given an opportunity to read the consent. If they wish to participate, they will be asked to sign the consent.

Participants will be randomized to receive liposomal bupivacaine or plain bupivacaine in a permuted block fashion, in block of sizes 2 or 4. For each block, block size will be selected uniformly at random. This method of randomization ensures balance between groups following every second or fourth allocation. The patients will be randomized after providing written informed consent in the outpatient clinic. Following randomization, the plastic surgeons performing the surgery and assessments will be blinded to study treatment arm. Patients will also be blinded to the study treatment arm. The anesthesia team and some of the ancillary research staff will not be blinded to study treatment arm.

Study Procedures

Patients randomly assigned to the liposomal bupivacaine group or plain bupivacaine group will receive this intervention intra-operatively prior to the initiation of surgery.

Local analgesia (TAP blocks) will be administered under ultrasound guidance in the operating room after the patient is intubated and under general anesthesia. Transfascial injections will be performed by the anesthesiologist using an epidural needle. Under sterile conditions and ultrasound guidance, the fascial plane between the internal oblique and transversus abdominis muscles (muscles of the abdominal wall) will be identified at the anterior axillary line, midway between the costal margin and iliac crest. The epidural needle will be inserted through the skin to the appropriate fascial plane, and the local anesthetic will be injected in that plane. Then the needle will be removed and discarded, and the patient will be prepped and draped to start the surgery.

Liposomal bupivacaine group: 20mL of Exparel® 1.3% mixed with 20mL of 0.25% bupivacaine, for a total of 40mL of local anesthetic mixture, 20mL to be injected on each side.

Regular bupivacaine group: 20mL of 0.25% bupivacaine injected on each side.

The Anesthesia team will follow standard care procedures regarding perioperative pain management (including preoperative, intraoperative, and postoperative analgesic regimens). Patients in all groups will also receive instructions in the preoperative period dictating the recommended approach to postoperative pain control.

Risks

Injection with the local anesthetic may cause participants to experience some discomfort, redness or a small bruise at the site of the injections. These will be temporary and will disappear in a couple of days.

With any nerve block there is a very small possibility of damage to the nerve, which could result in numbness of the surrounding area. According to the medical literature the likelihood of this injury is 1 in 10000 to 1 in 100000.

In rare cases the local anaesthetic may be absorbed into the bloodstream. In such rare scenario, the systemic absorption of the local anaesthetic may cause one of the following side effects:

- Slow-irregular heartbeats, low blood pressure, abnormal heartbeats, and cardiac arrest (2.3 events every 100,000 patients).
- Toxicity to the brain, including seizures (13.7 events every 100,000 patients);
- Respiratory arrest (4.6 events every 100,000 patients).

The blocks are performed in a monitored setting in the operating room. Patients are connected to monitors including blood pressure cuff, ECG and oxygen saturation. These monitors allow close monitoring for any signs of local anesthetic toxicity. The area is equipped with all resuscitation medication and equipment, and personnel are adequately trained in treatment of these complications.

Blocks are performed under direct ultrasound guidance so full visualization of the needle and the local anesthetic is observed. This will protect against nerve injury.

Reporting of Adverse Events or Unanticipated Problems involving Risk to Participants or Others; Study Withdrawal/Discontinuation

The progress of the study will be discussed formerly at regularly scheduled research meetings. These will serve as a forum for the voicing of concerns or problems with the study. If participant safety is a concern, the research investigators will immediately notify the P.I. Adverse events will be reported to the IRB according to IRB policies and procedures, as there are specific guidelines at IRB Policy and Procedure III.L.1 that must be followed.

Local anesthetic toxicity or nerve injury will be considered serious adverse events. Also allergic reactions to the local anesthetic will be considered adverse events. These patients will be withdrawn from the study and appropriate treatment will be instituted. The anesthesia care team will identify such an event and report it.

Statistical Considerations

Sample size calculations were based on demonstrating superiority of the TAP block with liposomal bupivacaine.

The sample size calculation for the oral morphine equivalent requirements was based on one of our previous studies on Enhanced Recovery Pathway for free flap breast reconstruction. Calculations showed that randomizing 60 patients will obtain 80% power to detect a difference between the two groups.

Privacy/Confidentiality Issues

Collected data will be stored in a password protected REDCap™ database with sole access delineated by the investigators and study personnel of the study.

Follow up and Record Retention

The data will be extracted from the EMR via of EPIC (eStar) and entered in a RedCap™ database. Paper copies of the surveys will be kept in a locked cabinet by the investigators of the study until study completion of all data analysis and then subsequently securely destroyed.

Collected data will include demographics, amount of supplemental postoperative narcotic analgesia both intravenous and oral, visual analog pain scale, time to return of bowel function, time to first opiate use, incidence of narcotic complications, and Quality of Life. Some of these variables will be collected at several times points as described above.

Records will be retained for 6 years following the study completion.

References

Practice guidelines for acute pain management in the perioperative setting. A report by the American Society of Anesthesiologists Task Force on Pain Management, Acute Pain Section. *Anesthesiology*. 1995; 82(4):1071-81.

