Study Title: Double-Blinded Randomized Control Trial Comparing Liposomal Bupivacaine and Plain Bupivacaine in Transversus Abdominis Plane For Deep Inferior Epigastric Artery Perforator (DIEP) Flap Breast Reconstruction

NCT # 03700970

Document date: October 1, 2018

Statistical Analysis

Patient characteristics were summarized as appropriate, using mean (standard deviation [SD]) and median (25th-75th interquartile range [IQR]) for quantitative variables and counts (percentages) for qualitative variables. Unadjusted comparisons of patients between the plain bupivacaine group and the liposomal bupivacaine group were performed using Wilcoxon test or Pearson chi-square test. The effect of the study intervention on daily oral opioid intake in oral morphine equivalents (OME) was examined using linear mixed effects regression model, adjusting for post-operative day (as a categorical variable), intervention status (plain bupivacaine/ liposomal bupivacaine), and their interaction. Since there were repeated measurements of OME for 7 post-operative days, a random intercept indexed by subject number was used in the linear mixed effects regression model. All analyses were performed using the R Programming Language 3.3.0 (R Foundation for Statistical Computing, Vienna, Austria). P<0.05 was considered a statistically significant difference.

Sample size calculations were based on demonstrating superiority of the TAP block with liposomal bupivacaine. A simulation-based power analysis was used to evaluate statistical power under the following assumptions: 1) use of linear mixed effects regression after log transformation of the opioid intake outcome, 2) average opioid consumption on days 0, 1, 2, and

3 is 30, 90, 70 mg mEq under standard of care, 3) use of liposomal bupivacaine will result in a 20% reduction in opioid consumption at each study day, and 4) the between- and within-subjects coefficients of variation are 20% and 60%, respectively (these values are based on standard of care data from our institution). Thus, the minimum-detectable difference is a 20% reduction in average opioid consumption at each study day. Under these assumptions, 60 participants are needed to achieve 80% power.

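### Daily pain scores stop at discharge and resume only on postoperative day 7, although discharged patients are already telephoned every day

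*Protocol*

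**What the plan says.** Protocol, Rationale and Specific Aims, secondary aim 1, schedules NPS in the PACU, then "on the day of surgery and all subsequent postoperative days until discharge and on postoperative day 7". The detailed scores follow the same rule: "For the inpatient postoperative days and postoperative day 7, patients will be asked to record their average, current, and maximum" NPS for the preceding 24 hours. The POD 7 score therefore looks back one day and does not cover earlier days at home.

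The other daily outcomes do not stop at discharge:

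- **Opioid use (primary aim):** "The amount of postoperative analgesia will be documented daily until postoperative day 7", obtained after discharge "with daily phone calls after the patients get discharged with instructions to document this data daily".
- **Opioid complications (secondary aim 4):** "defined as the number of occurrences of the complication per day for the first 7 days after surgery".
- **QoR-15 (secondary aim 5):** scheduled for days 0 to 7.

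The SAP (Statistical Analysis) names no analysis of pain. Its repeated-measures model, in which "a random intercept indexed by subject number was used in the linear mixed effects regression model", is for opioid intake. The only general provision is: "Unadjusted comparisons of patients between the plain bupivacaine group and the liposomal bupivacaine group were performed using Wilcoxon test or Pearson chi-square test". Neither document says how pain on days after discharge is to be handled, and neither gives discharge criteria or a length-of-stay distribution.

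**The concern.** Between the first discharges and POD 6, whether a patient has a pain score depends on an event after randomisation. A comparison of the available daily scores would then be made in a shrinking group that randomisation no longer protects. It would be biased if discharge depends on pain and the treatment arm affects pain or discharge. The protocol's Background makes such a link plausible: it argues that fewer opioid side effects speed recovery, and adds "This in turn can lead to decreased length of hospital stay".

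Pain is the first secondary aim and is needed to read the primary result. Less opioid at equal pain is a different finding from less opioid at more pain. The opioid comparison covers POD 0 to 7, but for part of that period the matching pain data would be missing for everyone already at home. The error could go either way: a true benefit could shrink, or a false difference could appear against the arm discharged earlier.

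**Working it through.** **The plan's own figure.** There is none for pain. The only sample-size statement is 60 participants for 80% power on opioid intake. It is used here only for the group size: 60 in balanced blocks is about 30 per arm.

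**Assumed inputs, because the documents give none.** NPS SD 2 points; true difference 1.0 point in favour of liposomal bupivacaine on every day; within-patient correlation 0.3 to 0.6; discharge possible after POD 2.

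**Step 1: precision, with no assumption about bias.** The 95% half-width for one day's difference is 1.96 × SD × √(2/n), with n per arm:

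- all patients, n = 30: 1.96 × 2 × √(2/30) = 1.01 points
- half in hospital, n = 15: 1.96 × 2 × √(2/15) = 1.43 points
- a quarter in hospital, n = 7.5: 1.96 × 2 × √(2/7.5) = 2.02 points

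In SD units, the difference detectable on one day with 80% power (two-sided 0.05) is (1.96 + 0.84) × √(2/n): 0.72 SD with all patients, 1.02 with half and 1.45 with a quarter.

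**Step 2: bias, a check by hand.** Let r be the correlation between pain and the tendency to remain in hospital, with half of the control arm still inpatient. The arms differ by 1.0/2 = 0.5 SD in pain. With λ(x) = φ(x)/(1 − Φ(x)), the benefit seen among inpatients is 1.0 − 2r[λ(0.5r) − λ(0)], where λ(0) = 0.798:

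- r = 0: 1.0, no bias
- r = 0.3: 1.0 − 0.6 × (0.896 − 0.798) = 0.94
- r = 0.6: 1.0 − 1.2 × (0.998 − 0.798) = 0.76

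**Step 3: bias, day by day.** Simulation with 300,000 patients per arm and setting. Control means were 6, 6, 5.5, 5, 4.5, 4, 3.5 and 3 for POD 0 to 7, the liposomal arm was 1 point lower, and scores were clipped to 0-10. From POD 3 a patient leaves with a daily probability set by whether the previous day's score was at or below a threshold (4 or 5). Clipping brings the true difference to 0.97-0.99, 0.96-0.98 and 0.95-0.96 on POD 3, 4 and 5. Attenuation in a simple comparison of inpatients:

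| Daily chance of leaving, at or below vs above threshold | POD 3 | POD 4 | POD 5 |
|---|---|---|---|
| 50% vs 50% (unrelated to pain) | about 0 | about 0 | about 0 |
| 60% vs 40% | 1-5% | 1-7% | 0-10% |
| 75% vs 25% | 5-13% | 6-25% | 9-32% |
| 100% vs 0% (extreme) | 15-38% | 26-52% | 31-57% |

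**Step 4: the reverse case.** No true pain difference, but comfortable patients leave at 75% per day in the liposomal arm and 50% in the control arm (25% in both above the threshold). A false difference against the liposomal arm appears: 0.07-0.25 points on POD 3, 0.16-0.46 on POD 4 and 0.24-0.62 on POD 5.

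**Step 5: would a model repair it?** A likelihood-type fit to all recorded scores (generalised least squares with the compound-symmetry covariance that a random intercept implies; true difference 1.0, unclipped, 200,000 per arm) gives 0.98-1.03 if discharge depends on the previous day's recorded score. If it depends on that day's unrecorded pain, the fit gives 0.83-1.02 under the 75/25 rule and 0.43-0.74 under the 100/0 rule.

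**The case against.** The strongest reply is that no planned analysis is shown to be biased. The SAP specifies none for pain, so the harm needs an analyst who chooses a simple inpatient comparison. The attenuation in step 3 is also the case that a mixed model repairs, because discharge there depends on a recorded score. Both points are correct, and the table should be read as an illustration of a simple analysis. They do not remove the gap: the model falls short when discharge follows unrecorded pain, and no model recovers the precision of scores never collected.

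Bias is also small beside noise. Under the 75/25 rule about 9-12 control and 6-9 liposomal patients would remain on POD 4. The half-width is then 1.96 × 2 × √(1/12 + 1/9) = 1.73 to 1.96 × 2 × √(1/9 + 1/6) = 2.07 points, against a bias of about 0.06-0.25. This stands, and makes precision the firmer consequence.

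Every decisive input is assumed. If patients stay until about POD 5, the gap is a day or so; if the benefit ends before POD 3, the attenuation figures do not apply. The reverse case needs a sizeable difference in discharge between arms although patients and surgeons are blinded. These points limit the size that can be claimed, not the existence of the gap.

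Finally, some research staff are unblinded and the documents do not say who telephones. That is a fair caution for the fix, though it applies equally to the opioid calls already planned, and pain is self-reported by blinded patients.

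**Conclusion.** The concern holds. The text establishes that pain is unrecorded from discharge to POD 6 while the other daily outcomes continue to day 7. Loss of precision over those days is certain once patients start to leave; its size depends on length of stay, which is not given. Bias is conditional on discharge being related to pain and on the arm affecting pain or discharge. Under the assumed inputs it runs from about nil to 57% attenuation at the extreme, and it can also produce a false difference where none exists. PACU, the day of surgery, the days before the first discharge, POD 7 and the primary opioid endpoint are not affected. This is a weakness in a secondary outcome that is cheap to correct and should be corrected: scores not collected at the time cannot be recovered later.

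**What to change.** Ask for average, current and maximum NPS on the daily calls already made after discharge, so that every randomised patient has daily scores from POD 0 to POD 7. State in the SAP that the arms are compared on all randomised patients, for example with the same form of repeated-measures mixed model as for opioid intake (day, arm and their interaction, random intercept per patient). The model without the added scores would be only a partial remedy.

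The cost is three questions per call and a minor amendment, with no extra visits. Calls become slightly longer, and scores change from in-hospital to telephone reporting at discharge, so the mode should be recorded with each score. Where staffing allows, the caller should be blinded to arm.

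### Time to return of bowel function has no end event, no stated source after discharge and no censoring rule, so patients who go home first may have no recorded value

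*Protocol*

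**What the plan says.** The protocol's Rationale and Specific Aims defines secondary aim 3 as "Time to return of bowel function: time from end of surgery (i.e. patient went to recovery or ICU", and the item ends there. Aim 2, directly above it, has the same start but is complete: "Time to first opiate use: time from end of surgery (i.e. patient went to recovery or ICU) until time of first opioid intake". No other section of either document defines return of bowel function.

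On sources, Follow up and Record Retention states "The data will be extracted from the EMR via of EPIC (eStar) and entered in a RedCap™ database". It then lists the variables, including "visual analog pain scale, time to return of bowel function, time to first opiate use, incidence of narcotic complications, and Quality of Life", and gives bowel function no source or time window of its own. Contact after discharge is described under the primary aim, for the amount of opioid: "It will be obtained from the medical records during hospitalization, and with daily phone calls after the patients get discharged".

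The SAP does not mention bowel function. For unadjusted comparisons it offers the Wilcoxon and Pearson chi-square tests, and for daily opioid intake a linear mixed model. It has no time-to-event method and no rule for a patient whose event is not observed.

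**The concern.** There are two linked problems.

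First, first flatus and first bowel movement are different events. Without a named end event, two abstractors can record different times for the same patient.

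Second, if the time is taken from the hospital record alone, it exists only for patients whose bowel function returned before they left. The times lost are then the long ones. A rank test on what remains compares two distributions that have each been cut at discharge. Discharge need not be a neutral cut: the protocol's Background expects fewer opioid side effects, constipation among them, to speed recovery and shorten the stay. The endpoint bears directly on that rationale, so a distorted result would matter to anyone reading the secondary findings.

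**Working it through.** **What the documents supply.** They give no expected time to bowel function, spread, treatment effect, length of stay or missing share for this endpoint, so there is no plan figure to reproduce. The one design figure, 60 participants for 80% power, concerns opioid intake. From it I take only 30 patients per arm, since randomisation in balanced blocks implies equal allocation. Everything else below is assumed.

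**Mechanism, by hand.** Let times be lognormal with median m and log-SD s, and let every patient be discharged at time d. The mean of the recorded times is

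m·exp(s²/2) · Φ[(ln(d/m) − s²)/s] / Φ[ln(d/m)/s].

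Assume s = 0.5, d = 72 h, a plain-arm median of 48 h and a liposomal median 20% shorter, 38.4 h.

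- True difference in means: 0.2 × 48 × exp(0.125) = 10.9 h.
- Plain arm, recorded: 54.4 × 0.622/0.791 = 42.8 h; 21% have no value.
- Liposomal arm, recorded: 43.5 × 0.776/0.896 = 37.7 h; 10% have no value.
- Recorded difference: 5.1 h, a ratio of 0.47 to the truth.

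**Simulation.** Here time is T = m·exp(0.4Z), with Z standard normal, and discharge C is normal with SD 18 h. A time is recorded only if T ≤ C. Patients without a recorded time are dropped and the arms compared by two-sided Wilcoxon test at 0.05, with 30 per arm and 4,000 trials per row. Medians and discharge means are in hours, plain v liposomal.

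| True medians | Mean discharge | No value, plain v liposomal | Median difference, true → recorded | Rejection rate, all times → recorded times |
|---|---|---|---|---|
| 72 v 54 | 84 both | 38% v 18% | 18 → 10.1 | 76% → 42% |
| 72 v 54 | 96 both | 27% v 11% | 18 → 11.7 | 75% → 51% |
| 72 v 54 | 120 both | 12% v 3% | 18 → 14.6 | 77% → 64% |
| 48 v 36 | 96 both | 7% v 2% | 12 → 10.7 | 76% → 69% |
| 36 v 27 | 96 both | 2% v 0.3% | 9 → 8.7 | 76% → 74% |
| 72 v 72 | 96 both | 27% v 27% | 0 → 0 | 5% → 5% |
| 72 v 72 | 96 v 72 | 27% v 52% | 0 → 7.1 | 5% → 18% |
| 72 v 54 | 96 v 72 | 27% v 29% | 18 → 15.9 | 75% → 79% |

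The first four rows lose 44%, 35%, 19% and 11% of the difference (for example 1 − 10.1/18 = 0.44), and the fifth loses 3%. In the seventh row there is no true effect, yet the liposomal arm appears about 7 h faster because its patients leave earlier and its long times are cut more often.

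**Wider inputs.** With times 20% shorter on liposomal bupivacaine, plain-arm medians of 48 or 72 h, log-SD 0.35 to 0.7 and equal discharge at 60 to 120 h, the recorded difference in means is 0.12 to 0.97 of the truth and the difference in medians 0.19 to 0.99. If discharge always waits for bowel function, the ratio is 1.

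**Follow-up to day 7.** Taking day 7 as 168 h, and with medians of 72 v 54 h, 1.7% and 0.2% of patients still have no event. Power with times capped there matches full observation (75% to 77%).

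**The case against.** The strongest reply is that the documents nowhere say collection of bowel function stops at discharge, and this is correct. Paper surveys are kept as well as EMR data. Patients are telephoned daily to day 7, QoR-15 is collected on days 0 to 7, and narcotic complications, constipation among them, are "defined as the number of occurrences of the complication per day for the first 7 days after surgery". A reader might infer that patients discharged early are certain to have no value. The documents support only that they may have none, because the source after discharge is unstated. The daily constipation count does not close the gap, since it gives no time of return.

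A reader might also infer that the difference between arms is roughly halved. That figure can be produced, as the hand calculation shows, but it depends wholly on assumed inputs. With early bowel function or late discharge the loss is negligible.

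A third tempting inference is that the bias runs toward no difference. That needs similar discharge times in the two arms. The protocol's own rationale allows the liposomal arm to leave sooner, and the bias can then create or inflate a benefit.

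Finally, neither document says that patients without an event will be dropped. That is true. However, the SAP offers no method that would keep them as censored, and a Wilcoxon test on recorded times leaves them out.

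**Conclusion.** The gap holds in this form: secondary aim 3 has a start and no end event, no stated source after discharge, and no time-to-event method or censoring rule. Patients who go home before bowel function returns may have no recorded value, and an analysis of recorded times alone would be truncated at discharge.

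The 10% to 45% shrinkage rests on lognormal times, a 25% shorter median on liposomal bupivacaine, equal discharge times and a complete-case analysis. With unequal discharge (96 v 72 h) and no true effect, the same analysis rejects in about 18% of trials. These are illustrations of what can happen, not estimates for this trial.

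The trial is powered on opioid intake, whose collection after discharge is stated, so the primary conclusion is untouched. This is a cheap improvement to a secondary endpoint.

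**What to change.** 1. In aim 3, name one end event that applies to every patient in and out of hospital, for example first bowel movement.
2. Record its date and time from the chart during the stay. For patients discharged without it, ask for the date and time in the daily calls already planned to day 7, and say so in the protocol.
3. In the SAP, specify a time-to-event analysis: Kaplan-Meier curves with a log-rank test or Cox model, censored at day 7 or last contact if earlier. Do not censor at discharge, because discharge may itself depend on recovery. Report by arm how many patients were discharged before the event.

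The cost is one question in an existing call and a few lines of text. The downside is some recall error in times reported after discharge.
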